7.3 Procedure-related Risks

We do not expect additional safety concerns from this protocol over those incurred during navigation bronchoscopy and CT-guided biopsy, explained to all patients undergoing navigation bronchoscopy and CT-guided biopsy as part of clinical informed consent in the standard of care setting. These risks, inherent in the procedures themselves, include pneumothorax, bleeding, pain, or, rarely, infection. Risk of death is estimated around 1/10,000. We do not expect that enrollment in this study will result in an increased risk for the patient.

The greatest risks from bronchoscopy are related to sedation and maneuvering the bronchoscope into the patient's airway. Accordingly, a nurse and/or a respiratory therapist will monitor all patients during the procedure and full anesthesia support will be available. In addition, pulse oximetry, respiratory rate, blood pressure, ECG, and heart rate will be continuously monitored. Patients will not be released until they are fully awake and medically stable as per standard local standard of care operations.

Other risks include those associated with biopsy and are the same as for standard flexible bronchoscopy: pneumothorax, breathing difficulty, vocal cord spasm, vomiting, dizziness, bronchial spasm, infection, low blood oxygen, heart attack and bleeding from biopsied site. The occurrence of these risks is extremely low. The measures to mitigate the risks are the same as for all bronchoscopy. To minimize the chance of bleeding, all patients will be questioned about tendency to bleed prior to bronchoscopy as per standard care. Anticoagulation with antiplatelet agents will be held according to guideline recommendations for that drug. If bleeding occurs, patients will be treated with direct pressure, local instillation of iced saline or other bronchoscopic interventions as deemed necessary. Vocal cord spasm will be mitigated with the use of lidocaine on the vocal cords. Patients with lung disease may receive bronchodilators prior to bronchoscopy at the discretion of the performing bronchoscopist. Patients are given supplemental oxygen and their oxygen level is continuously monitored using pulse oximetry. If there is any sign of a worsening in status, such as elevated heart rate, low oxygen, or electrocardiogram (ECG) changes, the procedure will be aborted.

The risks associated with CT-guided biopsy include pneumothorax, breathing difficulty, infection, low blood oxygen, and bleeding from biopsied site. The predominant risk of this procedure is pneumothorax. The measures to mitigate the risks are the same for all biopsy procedures. To minimize the chance of bleeding, all patients will be questioned for their tendency to bleed prior to the procedure as per standard care.

Anticoagulation with antiplatelet agents will be held according to guideline recommendations for that drug. If bleeding occurs, patients will be treated with direct pressure. Patients are given supplemental oxygen and their oxygen level is continuously monitored using pulse oximetry. A nurse, respiratory therapist and physician continuously monitor patients ECG, heart rate, blood pressure, and blood oxygen during the procedure. If there

CONFIDENTIAL

is any sign of a worsening in status, such as a clinically significant elevated heart rate, low oxygen saturation, or ECG changes, the procedure will be aborted.

7.4 Research-only Risks

Every effort will be made to protect the privacy of research subjects. Subject names and protected health information (PHI) will be kept confidential to the extent possible and as required by applicable laws and regulations. All records and data related to the study will be maintained in a secure protected space, with access restricted to study personnel or individuals designated by study personnel who (i) need access to the information to fulfill the terms and obligations of the Coordinating Site or the Sponsor under the Protocol and (ii) are under the same obligations as study personnel to keep the information confidential.

7.5 Benefits

There is no guarantee that the subjects will receive any benefit from this study.

7.6 Definitions

7.6.1 Adverse Event (AE)

An adverse event is any undesirable sign, symptom or medical condition or experience that develops or worsens in severity after starting the first dose of study treatment or any procedure specified in the protocol, even if the event is not considered to be related to the study.

Abnormal laboratory values or diagnostic test results constitute adverse events only if they induce clinical signs or symptoms or require treatment or further diagnostic tests.

7.6.2 Serious Adverse Event (SAE)

A serious adverse event is an undesirable sign, symptom or medical condition which:

- Is fatal or life-threatening;
- Requires or prolongs inpatient hospitalization;
- Results in persistent or significant disability/incapacity;
- Constitutes a congenital anomaly or birth defect; or
- Jeopardizes the participant and requires medical or surgical intervention to prevent one of the outcomes listed above.

Events **not** considered to be serious adverse events are hospitalizations for:

- Routine treatment or monitoring of the studied indication, not associated with any deterioration in condition, or for elective procedures.
- Elective or pre-planned treatment for a pre-existing condition that did not worsen.
- Emergency outpatient treatment for an event not fulfilling the serious criteria outlined above and not resulting in inpatient admission.

CONFIDENTIAL

- Respite care.

7.6.3 *Expectedness*

Expected: Expected adverse events are those that have been previously identified as resulting from administration of the agent. For the purposes of this study, an adverse event is considered expected when it appears in the study protocol or current adverse event list, in applicable information describing use of a marketed product in the standard of care setting (e.g. product manual, investigator's brochure, package insert) or is included in the informed consent document as a potential risk.

Unexpected: An adverse event is considered unexpected when it varies in nature, intensity or frequency from information provided in the study protocol or current adverse event list, in applicable information describing use of a marketed product in the standard of care setting (e.g. product manual, investigator's brochure, package insert) or when it is not included in the informed consent document as a potential risk.

7.6.4 *Attribution*

Attribution is the relationship between an adverse event or serious adverse event and participation in the study. Attribution will be assigned as follows:

- Definite – The AE is clearly related to study participation.
- Probable – The AE is likely related to study participation.
- Possible – The AE may be related to study participation.
- Unlikely – The AE is doubtfully related to study participation.
- Unrelated – The AE is clearly NOT related to study participation.

7.7 **Reporting Procedures**

7.7.1 *General Considerations*

Investigators should use correct medical terminology/concepts when reporting AEs or SAEs, and avoid colloquialisms and abbreviations. If known at the time of reporting, a diagnosis should be reported rather than individual signs and symptoms (e.g. record only liver failure or hepatitis rather than jaundice, asterixis, and elevated transaminases). However, if a constellation of signs and/or symptoms cannot be medically characterized as a single diagnosis or syndrome at the time of reporting, it is acceptable to report the information that is currently available. If a diagnosis is subsequently established, it should be reported as follow-up information.

All deaths that occur during the protocol-specified AE reporting period, regardless of attribution, will be reported to the appropriate parties. When recording a death, the event or condition that caused or contributed to the fatal outcome should be reported as the single medical concept. If the cause of death is unknown and cannot be ascertained at the time of reporting, report “Unexplained Death.”

CONFIDENTIAL

A pre-existing medical condition is one that is present prior to initiation of treatment or intervention specified by the protocol. Such conditions should be reported as medical and surgical history. A pre-existing medical condition should be re-assessed throughout the trial and reported as an AE or SAE only if the frequency, severity, or character of the condition worsens during the study. When reporting such events, it is important to convey the concept that the pre-existing condition has changed by including applicable descriptors (e.g., “more frequent headaches”).

Any AE that results in hospitalization or prolonged hospitalization should be documented and reported as an SAE. If a patient is hospitalized to undergo a medical or surgical procedure as a result of an AE, the event responsible for the procedure, not the procedure itself, should be reported as the SAE. For example, if a patient is hospitalized to undergo coronary bypass surgery, record the heart condition that necessitated the bypass as the SAE.

Hospitalizations for the following reasons do not require reporting:

- Hospitalization or prolonged hospitalization for diagnostic or elective surgical procedures for pre-existing conditions; or
- Hospitalization or prolonged hospitalization required to allow efficacy measurement for the study; or
- Hospitalization or prolonged hospitalization for scheduled therapy of the target disease of the study.

7.7.2 *Serious Adverse Events*

All serious adverse events, regardless of causality to study participation, will be reported to the Principal Investigator and/or the Study Coordinator at each institution, and also to the Coordinating Center.

All serious adverse events must be reported to the Coordinating Center within 24 hours of the investigator becoming aware of the event. Events should be reported using the Vanderbilt SAE form, located in the packet of supplemental forms. This form must be fully completed and emailed (preferred), faxed, or scanned to:

ATTN: VICC CTSR Personnel
EMAIL: [contact]
[contact]

If SAE documents are faxed, the Coordinating Center must be notified via email as well. Follow-up information must also be reported within 24 hours of receipt of the information by the investigator.

The Coordinating Center will disseminate information regarding serious adverse events to the participating sites as described in FDA guidance only in the case that the event(s) is/are unexpected, and is/are believed to be related (i.e., possibly, probably or definitely) to the study device/medication. The Coordinating Center will be responsible for reporting of events to supporters as appropriate (outlined below).

CONFIDENTIAL

7.7.3 *Institutional Review Board*

All adverse events and serious adverse events will be reported to the IRB per current institutional standards. If an adverse event requires modification of the informed consent, these modifications will be provided to the IRB with the report of the adverse event. If an adverse event requires modification of the study protocol, these modifications will be provided to the IRB as soon as is possible.

7.7.4 *Reporting to Funder*

Upon request from Medtronic, Vanderbilt University Medical Center acting as the Coordinating Center will notify Medtronic of any serious adverse event (SAE) that occurs during the reporting period as defined above in Section 7.2. Within 2 working days after the Coordinating Center initially receives the safety information from the site, the Coordinating Center will report the SAE (on the MedWatch, Medtronic, or Vanderbilt SAE form approved by the Coordinating Center and Medtronic) to a point of contact specified by Medtronic. Follow-up SAE reports received by the Coordinating Center should be sent within 2 working days to Medtronic using the same procedure used for transmitting the initial report.

8. Data Safety and Monitoring

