CONFIDENTIAL

VERITAS

THO 19102: NaVigation Endoscopy to Reach Indeterminate lung nodules versus Transthoracic needle Aspiration, a randomized controlled Study (VERITAS)

Principal Investigator:

[name]

Professor of Medicine and Thoracic Surgery
Associate Professor of Mechanical Engineering
Vanderbilt University School of Medicine

Co-Principal Investigator:

[name] DPhil MSc FRCP
Professor of Respiratory Medicine
Oxford Centre for Respiratory Medicine
Clinical Director, Oxford Respiratory Trials Unit
University of Oxford

Protocol Version 29MAR2023

CONFIDENTIAL

PROTOCOL SYNOPSIS

Title	Navigation Endoscopy to Reach Indeterminate lung nodules versus Transthoracic needle Aspiration, a randomized controlled Study
Short title	VERITAS
Study objective	In this study, we propose to study in a 1:1 randomized controlled trial the diagnostic accuracy of navigation bronchoscopy pathway with fluoroscopic navigation (F-Nav) using a non-inferiority study design (primary endpoint) versus the current clinical standard of care: CT-guided biopsy.
Study device	SuperDimension and Fluoroscopic navigation.
Design	Multicenter, randomized, non-inferiority study.
Study centers	Vanderbilt University Medical Center, and approximately 5 to 7 additional sites based in the United States.
Number of subjects	N=258
Subject follow-up	Patients with non-diagnostic biopsy or benign diagnoses will be followed for up to one year as part of the study with further diagnostic procedures as clinically required.

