4.7 Comparison: CT-guided Biopsy Pathway

The control arm of the study will consist of CT-guided biopsy, which will be performed by interventional radiologists with expertise in transthoracic needle biopsy and/or fine needle aspiration (as defined by more than 25 procedures performed in the past two years as a department). Procedures will be performed in a dedicated interventional CT scanner with multi-slice capabilities. Patient analgesia with local anesthesia and moderate conscious sedation will be used. Biopsy number, core biopsy vs. fine needle aspiration, use of coaxial needles, and use of rapid on-site cytologic examination will be at the discretion of the proceduralist per local institutional preferences. Procedures will be followed by limited CT scan and/or chest radiograph to exclude pneumothorax if required per local standard of care. The procedure will be deemed non-diagnostic if the proceduralist is unable to reach the nodule or if a complication occurs and therefore no biopsy is obtained.

- 1. Patients not eligible for general deep sedation and general anesthesia and therefore not eligible for bronchoscopy, but potentially eligible for CT-guided biopsy, will be excluded from the study but recorded as such in the CONSORT diagram.**
- 2. Patients randomized who fail to present for their assigned intervention will be considered screen-failure**
- 3. Patients randomized who present for their assigned intervention but do not undergo the procedure for reasons other than for contraindications to the procedure (per institutional policy) will be analyzed as non-diagnostic procedure, and otherwise considered screen-failure. The cause for cancellation will be recorded in the case report form.**

CONFIDENTIAL

See Procedural Flow Chart (Section 14).

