6.2 Analysis plan

Analytic populations

The analysis set will be the per-protocol (PP) population, which yields more conservative estimates for the noninferiority objective than the intention-to-treat (ITT) population. The ITT analysis will include every randomized subject assigning a treatment failure for those who drops out without the final data. The ITT analysis will be a secondary, sensitivity analysis.

Prior distribution

The probability of successful diagnostic accuracy for each treatment arm will be modeled with a Beta-Binomial distribution. A non-informative prior Beta (1,1) will be used for both treatment arms.

Interim analysis

No interim analysis is planned for this trial. Interim analyses typically assess for futility and efficacy stops regarding the primary outcome part-way through a trial. However, the primary outcome of diagnostic accuracy requires up to 12 months of radiographic follow-up in patients not determined to have malignant nodules by study biopsy. Therefore, an analysis of this outcome halfway through accrual could not be performed until one year after that enrollment midpoint was reached, at which time we expect enrollment to be complete for the entire planned accrual. An interim analysis of the primary endpoint is therefore impracticable. Interim analyses for safety endpoints are often commonly performed in investigations of new devices or novel interventions, but as both study procedures represent long-standing standard of care options for the tissue sampling of lung nodules, complications of these procedures themselves are not considered risks unique to this research. The primary risk to participation in this research involves patient privacy and confidentiality, any breach of which will be reported to the PI and appropriate regulators on an ongoing basis as described later in this protocol, which does not require interim analysis.

Final analysis

The final analysis will be conducted when data from all randomized patients are available (n=112 per group). The conclusion will be based on the final posterior distributions (n=112 each). We will conclude noninferiority of NB compared to CT if the estimated probability of inferiority is less than 5%. We will conclude superiority of NB if the estimated probability that NB is better than CT is higher than 95%.

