7.2 Reporting Period

The procedures being performed, bronchoscopy and CT-guided biopsy, are standard of care for management of indeterminate pulmonary nodules. Therefore, collection of data regarding adverse events and serious adverse events will be limited in this study:

- Any serious or non-serious adverse event related to research procedures (i.e. the consent process, HIPAA compliance, etc.) will be collected.
- After informed consent but prior to initiation of navigation bronchoscopy or CT-guided biopsy, serious and non-serious adverse events should be reported only if possibly, probably or definitely attributed by the patient's study physician to a protocol-mandated research procedure or intervention.
- The principal AE reporting period will be within 7 days of the study procedure, as it would be exceedingly uncommon for a new biopsy-related complication to occur more than 7 days after the biopsy procedure. Effort should be made on post-procedure day #7 to assess for any complications which have not already risen to investigator awareness.
- Any serious adverse event that occurs \leq 7 days after initiation of navigation bronchoscopy or CT-guided biopsy, regardless of causality to participation in the study, must be reported to the Coordinating Center in an expedited fashion as directed below (Reporting Procedures).

CONFIDENTIAL

During the 7-day reporting period, non-serious adverse events should only be recorded if, in the opinion of the investigator, there is a reasonable possibility the event is attributable to participation in the study. Non-serious adverse events related to navigation bronchoscopy or CT-guided biopsy or the next phase of the patient's treatment or management should NOT be recorded.

Participants should be instructed to report any serious post-study event(s) that might reasonably be related to participation in this study. The investigator should notify the IRB and the Coordinating Center of any unanticipated death or adverse event occurring after a participant has discontinued or terminated study participation that may reasonably be related to the study.

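### The site-notice rule for unexpected SAEs refers to the study device or medication, so read literally it cannot cover CT-guided biopsy, and it does not match the attribution scale

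*Combined protocol and SAP*

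**What the plan says.** Section 7.7.2 sets two conditions for telling participating sites about an SAE. Information goes out "only in the case that the event(s) is/are unexpected", and in addition the event must be one that "is/are believed to be related (i.e., possibly, probably or definitely) to the study device/medication".

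The synopsis gives the study device as "SuperDimension and Fluoroscopic navigation". Section 4.7 states: "The control arm of the study will consist of CT-guided biopsy". That arm does not use the named platform, and no section defines a study medication.

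Section 7.6.4 uses a different reference for causality: "Attribution is the relationship between an adverse event or serious adverse event and participation in the study". All five grades repeat it; the lowest reads "The AE is clearly NOT related to study participation".

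Two other sections bear on how a site might apply that scale. Section 7.2, on the 7-day reporting window, says: "Non-serious adverse events related to navigation bronchoscopy or CT-guided biopsy or the next phase of the patient's treatment or management should NOT be recorded". Section 6.2, explaining why no interim safety analysis is planned, says that "complications of these procedures themselves are not considered risks unique to this research".

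**The concern.** The trial randomizes patients between two invasive procedures, and the synopsis plans about 5 to 7 sites besides the lead center. A rule for cross-site safety notices should work for both procedures. This one is written around a device that belongs to one arm and a medication that the trial does not have. If CT-guided biopsy caused a serious event of unlisted nature, intensity or frequency at one site, the rule as worded would not tell the others, which would go on randomizing patients to that procedure.

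The second problem is that the rule uses the terms possibly, probably and definitely from the attribution scale but applies them to something the scale does not grade. Sites could also reasonably disagree on whether harm from a standard-of-care biopsy counts as harm from taking part in the study. The grades would then not be comparable between sites.

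**Working it through.** The documents state no figure on this point and no arithmetic decides it. The check sets the passages side by side.

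| Section | What it decides | Reference for causality |
|---|---|---|
| 7.2 | Which non-serious events to record in the 7-day window | Participation (recorded), as distinct from the biopsy procedure (not recorded) |
| 7.6.4 | The grade for every AE and SAE | Participation in the study |
| 7.7.2 | Which SAEs are passed to the sites | Study device or medication |

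1. **Form of the rule.** Site notice = unexpected AND related to the study device or medication. The word only makes both conditions necessary. The mention of FDA guidance in the same sentence does not widen them within these documents.
2. **Can a CT-arm SAE be unexpected?** Yes. Section 7.6.3 counts an event as unexpected if it departs in nature, intensity or frequency from the protocol, the adverse event list or product information, or is absent from the consent form. Section 7.3 lists a limited set of CT-biopsy risks, so the category is not empty.
3. **Can a CT-arm SAE be related to the study device or medication?** Not on the literal text. The named device is the bronchoscopy platform. Section 4.7 provides for local anesthesia and moderate sedation, but nothing designates these as study medication, and harm from the needle would not be related to them in any case. The second condition fails and no notice follows.
4. **Bronchoscopy arm.** An SAE caused by the navigation platform can meet the condition. One caused by the general anesthesia in section 4.6, or by the biopsy tools, is not clearly covered.
5. **Does 7.6.4 supply the judgment that 7.7.2 needs?** No. It defines one scale, against participation. No section defines a grade against the device or the procedure.
6. **How would a site grade a biopsy-caused SAE under 7.6.4?** Two readings are open. Sections 6.2 and 7.2 treat procedural complications as part of standard care, which points toward unlikely or unrelated. Randomization assigns the procedure, however, and section 7.6.1 ties adverse events to procedures specified in the protocol, which points toward related. The text does not choose.
7. **Does another route tell the other sites?** Not directly. Under 7.2 and 7.7.2, SAEs within 7 days of the procedure go to the Coordinating Center within 24 hours whatever their cause. Section 7.7.3 covers the IRB, 7.7.4 the funder on request, and 8.2 quarterly DSMC review. Under 9.1, sites receive approved protocol amendments, but only if an event leads to one.

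**The case against.** The strongest case against is that this is a slip of wording with little consequence. Collection of SAEs does not depend on attribution. The DSMC sees all SAEs, can meet ad hoc and has authority to intervene. An event that leads to a protocol amendment reaches the sites that way. Both procedures are long-established, and limiting adverse event collection for that reason is a stated choice in 7.2. Serious unexpected events should be rare: with the risk of death of about 1 in 10,000 in section 7.3, 129 CT-arm patients give 129 × 1/10,000 = 0.013 expected deaths. All of this stands, and it limits the size of the point. It does not supply the missing notice.

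One sentence of 7.7.2 could be read as a remedy: it has all SAEs reported to the investigator or coordinator at each institution, whatever the cause. If that meant every institution for every event, the later restriction on dissemination would have no purpose. The natural reading is that each site's own events go to its own staff.

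A reader might go further and infer that biopsy-caused SAEs will be graded unrelated in both arms. The documents do not support that as more than a possibility. The sentence in 7.2 concerns non-serious events only, the one in 6.2 explains the absence of an interim analysis, and the opposite grading is equally open.

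A reader might also infer that the rule cannot be applied from the data collected. That does not follow. The SAE form is in a packet that is not part of these documents and may already hold a device or procedure field. Section 7.7.2 does not say who judges relatedness, so the Coordinating Center could do so from the report.

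**Conclusion.** The point holds as a limited defect in a stated rule. On its literal wording, the site-notice condition excludes every SAE caused by CT-guided biopsy, the procedure planned for 129 of the 258 patients. Its reference for causality also differs from the only one that the protocol grades. The 129 are patients exposed, not notices missed; the documents give no basis for estimating the latter. The conclusion rests on reading study device as the synopsis gives it and on there being no study medication.

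It is tempting to conclude that a between-arm difference in harm, such as chest tubes, would be hidden. The documents do not support this. No table of related SAEs is planned. Pneumothorax, chest-tube placement, bleeding requiring intervention and hospitalization are secondary endpoints with no attribution condition (section 4.8), and complications are recorded as procedural variables (section 6.3). Pneumothorax is a listed risk of both procedures, hence generally expected at known rates, and would ordinarily prompt no site notice under the present wording or a corrected one.

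The primary endpoint, sample size and error rates are not touched. The change is worth making because it is cheap and closes a gap in safety communication.

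**What to change.** Reconcile sections 7.2, 7.6.4 and 7.7.2 as follows.

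- **7.6.4:** grade the relation of each reported event to the randomized procedure performed, navigation bronchoscopy or CT-guided biopsy, including its sedation or anesthesia, on the same basis in both arms. Add a separate item for relation to research-only procedures.
- **7.7.2:** make the site-notice condition refer to that procedure grade instead of the study device or medication. State who makes the judgment.
- **7.2:** use the same terms, so that the distinction between participation and procedure is drawn once and consistently.

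The cost is wording in three subsections, one field on the SAE form if it is not already there, and possibly a few more site notices. No visit, treatment or clinical rule changes.
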